1.0 Objectives*

1.1 The purpose of this study is to determine if an isometric gluteal activation home exercise program (HEP) combined with a movement retraining program utilizing feedback cues produces significant changes in scores on the Forward Step-Down Test (FSDT) in healthy young adults with movement coordination impairments.

- SA1: To determine if an isometric gluteal activation HEP with a movement retraining program with feedback cues produces significant changes on scores FSDT compared to the gluteal activation HEP alone.
- SA2: To determine if an isometric gluteal activation HEP followed with a movement retraining program with feedback cues produces significant changes on category FSDT compared to gluteal activation HEP alone.
- SA3: To determine if an isometric gluteal activation HEP with a movement retraining program with feedback cues produces changes in the peak activation of the gluteus medius and gluteus max during the FSDT compared to the gluteal activation HEP alone.
- SA4: To determine if an isometric gluteal activation HEP with a movement retraining program with feedback cues produces changes in the mean activation of the glute med and glute max during the FSDT compared to the gluteal activation HEP alone.
- SA5: To determine if HEP dose has an effect on the FSDT response, as measured by change in score on the FSDT.

1.2

- SA1: FSDT
 - H_0 : An HEP focusing on isometric gluteal activation with a movement retraining program with feedback cues will have no change on FSDT score.
 - H_1 : An HEP focusing on isometric gluteal activation with a movement retraining program with feedback cues will change FSDT scores more than a gluteal activation program alone.
- SA2: FSDT
 - H_0 : An HEP focusing on isometric gluteal activation with a movement retraining program with feedback cues will have no change on movement quality categorization.
 - H_1 : An HEP focusing on isometric gluteal activation with a movement retraining program with feedback cues will have a greater change on movement quality category than the gluteal activation program alone.

- SA3: Peak Activation, FSDT
 - H_0 : An HEP focusing on isometric gluteal activation with a movement retraining program with feedback cues will not produce a significant change MVIC of the glute med and glute max.
 - H_1 : An HEP focusing on isometric gluteal activation with a movement retraining program with feedback cues will significantly change the peak MVIC of the glute med and glute max compared to the gluteal activation program alone.
- SA4: Mean Activation, FSDT
 - H_0 : An HEP focusing on isometric gluteal activation with a movement retraining program with feedback cues will not produce a significant change the mean MVIC of the glute med and glute max.
 - H_1 : An HEP focusing on isometric gluteal activation with a movement retraining program with feedback cues will significantly change the mean MVIC of the glute med and glute max compared to the gluteal activation program alone.
- SA5: Dose Response, FSDT
 - H_0 : Increased adherence to a HEP will not change scores on the FSDT or MVIC of glute max or glute med.
 - H_1 : Increased adherence to a HEP will significantly change scores on the FSDT and/or MVIC of glute max or glute med.

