- 2.2 Our participants will undergo a prescreening utilizing the FSDT. Preliminary data will be used for exclusion, stratification, and randomization of participants. The FSDT is scored on a 0–6-point scale with 0-1 categorically defined as good, 2-3 as moderate, and 4+ as poor movement quality. A participant will be excluded from the study if their score is defined as “good”. Then, stratification will be based upon the participant's categorical FSDT score of either moderate or poor to ensure equal representation of the category in each experimental group. Once stratification is complete, participants will be randomly assigned into two groups. The Control group will receive an HEP focusing on isometric gluteal activation while the Experimental group will receive an HEP focusing on isometric gluteal activation plus movement retraining program. This will be the first study on this topic by the authors. However, two of the authors have done prior research using the FSDT as an outcome measure.^{5,6} Similar FSDT and sEMG procedures will be used as in previous studies. In this investigation we will compare the effects of an isometric gluteal activation HEP vs an isometric gluteal activation plus movement retraining HEP. Outcome measures will include FSDT score and movement quality category, Gmed and Gmax mean and peak activation via sEMG, and compliance measures of both HEP's to evaluate dose response.
- 2.3 The FSDT is a commonly used clinical assessment tool for evaluating lower extremity (LE) strength and function.⁷ It specifically aims to assess postural control, neuromuscular control, and strength of the lower extremity.⁷ Previous studies have found that healthy individuals may not have proper neuromuscular control to manage excessive frontal plane motion during the FSDT.^{5,6} Research has not been conducted to examine how attempting to change or improve individuals' motor programs would affect their performance in the FSDT. Movement retraining could be a way to help improve frontal plane movement quality in individuals undergoing the

FSDT. Movement retraining is defined as a process in which a motor program is changed with the goal of reducing pain or injury risk.⁸

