Home Exercise programs (HEPs) provide a means to implement an interventional exercise plan to be conducted at the participant's home. Normally, an HEP consists of clear visuals and written instructions that guide the participants in completing the exercise effectively. In utilizing videos, as well as visuals and written instructions in the HEP for this study, the subjects will benefit from both visual and auditory cues given in video form. This combined with visual feedback given by the mirror in front of the participant provides knowledge of their execution of the movement. The cues combined with the knowledge of their performance will help to emphasize correct movement patterns. Research supports the idea that more feedback is not always more helpful when engaging in motor learning. Allowing participants to make and correct their own errors at home helps to support motor learning retention by allowing the participant to self-select the corrections to their movement patterns as they engage in the exercise.¹⁰ The participant is able to do this by attending to and correcting their movement patterns in the mirror as they recognize them. Additionally, the participants will have the ability to control the timing of their feedback. By allowing learner to decide the pace of feedback, evidence shows that it enhances engagement, confidence, and motor learning.¹⁴ However, HEP's rely on patient compliance. Patients are expected to adhere to the program and truthfully document a log of completion. To check compliance, the log can be monitored throughout the process as well as asking the participant to demonstrate the HEP from memory.

Gluteal activation from an isometric activation HEP alone has shown to increase performance on the forward step-down test. However, the improvement was not found to be clinically significant.^{7,8} The aim of this study would be to build on prior research and create a HEP that could be used to show a clinically significant difference in FSDT scores. Over the eight-week intervention, this approach will aim to utilize visual and auditory cueing used during functional dynamic exercises to improve hip activation by increasing postural control which would translate into meaningful improvements in FSDT scores and dynamic knee stability.

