9.0 Procedures Involved*

- 9.1 This study is a randomized control trial with stratification. Preliminary data from a preliminary FSDT will be used for exclusion, stratification, and randomization so that we can avoid any bias in results. The FSDT is scored on a 0–6-point scale with 0-1 categorically defined as good, 2-3 as moderate, and 4+ as poor. A participant will be excluded from the study if their score is defined as good or a 0-1 score. Then, stratification will be based upon the participant's categorical FSDT score of either moderate or poor to ensure equal representation of the category in each group. Participants will be randomly assigned to either the control group (hip activation HEP) or the experimental group (Hip activation plus movement retraining HEP). Individuals will receive their HEP protocol in an opaque envelope to ensure allocation concealment. The dependent variables are the FSDT score (statistical and clinical significance) and Gmed and Gmax sEMG activation (peak and mean).
- 9.2 Research procedures being performed and procedures being to monitor subjects for safety or minimize risks

Recruitment and Informed Consent Procedures

- Potential subjects will be recruited via word of mouth from people who are local to Shreveport, LA and local clinical/academic settings. Once they are recruited, meeting will be held for all potential participants to obtain informed consent. Then, the participant will complete a self-reported health questionnaire and a preliminary FSDT. If a potential participant cannot be

present at this meeting, a meeting will be scheduled with the investigators to obtain these measures.

- To ensure confidentiality, participants will be given a random identification number after their informed consent is obtained. Participant scores on the initial FSDT screening will be recorded by ID. Randomized stratification will take place following enrollment of all participants to ensure an equal distribution of FSDT scores between the control and experimental groups.
- Following enrollment, participants will sign up with their participant number for preliminary data collection in the motion analysis lab in room 2-217 in the SHPS at LSUHS. The participants will be instructed to wear shorts and advised to not wear leggings, tights, or pants or any lotions, both of which could impact EMG placement and data collection.

Anthropometric data collection procedures

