9.5 N/A

10.0 Data and Specimen Banking

10.1 N/A

10.2 N/A

10.3 N/A

11.0 Data Management and Confidentiality

11.1 Data analysis plan and statistical procedures.

FSDT

Data processing: Each participant will perform a pre- and post- intervention trial for the FSDT that will be scored. The FSDT consists of 5 repetitions of a step-down task. One score is given for the whole test. One raters will score the FSDT (MM).

Data analysis: For the FSDT data, a 2x2 repeated measures ANOVA will be performed with significance set at alpha = .05. Post hoc testing will be used if significant differences are detected with the ANOVA. Tukey's HSD test will be used as the post hoc test, with significance set at alpha = .05.

sEMG

Data processing: Raw sEMG signals will be bandpass filtered between 10-500 Hz. The signal will be rectified, then smoothed using the Root Mean Square method with a 50ms window. The signal from the FSDT and UPST will be normalized to the MVIC obtained during the MVIC testing.

Data analysis: Following MVIC normalization, sEMG activity will be recorded during each of the outcome measures. Each FSDT step-down repetition will be analyzed as a separate trial, and the mean and peak activation for GMax and GMed will be extracted from each of the 5 trials. A mean value for each variable (mean and peak activation of GMax, mean and peak activation of GMed) will be calculated and recorded at the pre-and post-test sessions.

For the sEMG data, a 2x2 repeated measures ANOVA will be performed for each measurement (mean, peak) for each muscle (Gmed, Gmax), with significance set at alpha = .05. Post hoc testing will be used if significant differences are detected with the ANOVA. Tukey's HSD test will be used as the post hoc test, with significance set at alpha = .05.

11.2 G* power (Heinrich-Heine-University Dusseldorf, Dusseldorf, Germany) software was used to perform a priori power analysis to determine the

required N for this investigation. Data from [name] Et Al. (2025) study reported a Cohen's d of 0.58 (d=0.58).⁵ An N of 26 was calculated to achieve significant results with beta= .80 and alpha =.05 for a two-tailed hypothesis from an interaction effect of the 2x2 repeated measures ANOVA. Assuming 20% attrition, plus an additional 10% for FSDT screening failures, a final N=38 is required for this study.

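### SA2 (FSDT category) has no analysis of its own, the one stated ANOVA ignores the stratification factor, and clinical significance has no pre-stated threshold

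*Combined protocol and SAP*

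**What the plan says.** Section 1.1 makes category change a separate aim: to learn whether the combined programme "produces significant changes on category FSDT compared to gluteal activation HEP alone". Section 1.2 gives SA2 its own hypotheses, the alternative being that the combined programme "will have a greater change on movement quality category than the gluteal activation program alone". Section 2.2 repeats that "Outcome measures will include FSDT score and movement quality category".

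The categories are defined in section 9.1: "The FSDT is scored on a 0–6-point scale with 0-1 categorically defined as good, 2-3 as moderate, and 4+ as poor". The lowest is closed at entry: "A participant will be excluded from the study if their score is defined as good or a 0-1 score". Sections 9.1 and 9.2 stratify randomisation on the remaining two categories, with equal numbers of control and intervention envelopes in each stratum.

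Section 11.1 then gives one analysis: "For the FSDT data, a 2x2 repeated measures ANOVA will be performed with significance set at alpha = .05", with Tukey's HSD as the post hoc test. It follows a statement that the whole test receives a single score. No ordinal model, rank test or comparison of proportions appears.

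On clinical significance, section 9.1 lists as a dependent variable "the FSDT score (statistical and clinical significance", and the end of the Background states the aim to "create a HEP that could be used to show a clinically significant difference in FSDT scores". No section gives a minimal important difference, a minimal detectable change, a responder definition or a decision rule.

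**The concern.** An analyst following section 11.1 has two choices for SA2: leave it untested, or code the three categories as numbers and put them through the 2x2 ANOVA. The second treats the codes as equally spaced and makes no use of baseline category, although the randomisation was built around it. When allocation is balanced within strata but the analysis ignores them, the error term still contains the variation in change that baseline category explains. The test is then conservative and loses power.

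The second gap is separate. The Background motivates the study by saying that earlier programmes did not lower the score by a clinically significant amount. An ANOVA p-value speaks to whether a mean difference is zero, not whether it is large enough to matter. With no threshold on paper, one could be chosen after the data are seen.

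**Working it through.** **1. The plan's own sample size.** Section 11.2 gives d = 0.58, alpha 0.05 two-sided, 80% power and N = 26 for the ANOVA interaction. Taking f = d/2 = 0.29, m = 2 measurements and pre-post correlation 0.5 (assumed; not stated):

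- lambda = f² × N × m / (1 − rho) = 0.0841 × 26 × 2 / 0.5 = 8.75, on 1 and 24 df. Power is 0.810, so N = 26 reproduces.
- 26 / (1 − 0.30) = 37.1, rounded up to 38, the stated final N.

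The evaluable number is therefore 13 per arm. The sizing concerns the score only. With f = 0.29 at this correlation, the implied between-arm difference in change is 4 × 0.29 = 1.16 SD. Effects of 0.58, 1.0 and 1.16 SD are used below.

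**2. The tests compared for SA2.**

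- ANOVA on the codes: in a 2x2 design the interaction test is the two-sample t-test on change in code, 24 df.
- Stratified mean-score CMH test on week-8 code: T = sum over strata of (observed total in the experimental arm − n₁ × stratum mean); variance = sum of (n₁n₀/n) × s²; T²/variance on 1 df.
- Linear model: week-8 code on arm and baseline category.

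**3. Simulation inputs.** From the documents: integer scores 0-6, entry at 2 or more, cut-offs 0-1 / 2-3 / 4+, arms balanced within baseline category, 13 per arm. Assumed: latent normal score with mean 3.2, SD 1.2, correlation 0.5.

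| Between-arm effect | ANOVA on codes, unadjusted | CMH stratified by baseline category |
|---|---|---|
| 0 (type I error) | 2-3% | about 5% |
| 0.58 SD | 20-21% | 26-27% |
| 1.0 SD | 56-57% | 64-65% |
| 1.16 SD | 71% | 77% |

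**4. Where the gain comes from.** Under the same assumptions with no change in the control arm, CMH against the adjusted linear model on the same codes gave 26% v 27%, 65% v 66% and 77% v 78%. The gain comes from using baseline category, not from leaving the linear model. In runs without balancing within strata, ANOVA on the codes held type I error at 4.5-5.1%.

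**5. Cost of the category itself.** In those unbalanced runs (assumed mean 3-3.5, SD 1-1.3, correlation 0.5, control improvement 0.3 points), at 1.16 SD, ANOVA had 77-80% power on the score and 62-71% on the category, a loss of about 8 to 15 points. A Fisher test on improving by a category had 43-54%. This loss comes from coarsening the score and no choice of test fully recovers it.

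**6. Precision of a responder comparison.** Assuming 33% v 55% improve by a category (illustrative rates; the documents give none):

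1.96 × √(0.33 × 0.67/13 + 0.55 × 0.45/13) = 1.96 × √(0.0170 + 0.0190) = 0.37.

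The 95% CI is about ±37 points around a 22-point difference, roughly −15 to +59.

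**7. Category shift against score change.** Under the protocol's cut-offs, 2 to 1 (one point) is a category improvement; 3 to 2 (one point) and 6 to 4 (two points) are not. A one-category shift is therefore not a fixed amount of score change.

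**The case against.** The strongest reply is that the phrase introducing the ANOVA may be meant to cover both score and category, in which case SA2 has a test, and one that does not exceed its nominal error rate. That stands in part. A reader might infer that SA2 has no valid test, or that ANOVA is the wrong tool for a three-level outcome. The documents and the figures do not support either: type I error is at or below 5%, a linear model with baseline category does as well as CMH, and unadjusted ANOVA on the codes was at least as powerful as an unadjusted rank-sum or Fisher test. What remains is that the plan does not say what is done for SA2 and that its one stated method leaves out the stratification factor.

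A reader might also infer that the trial cannot meet its purpose. Section 1.1 frames the purpose as significant change in FSDT scores, which the interaction test addresses. The aim of a clinically significant difference appears in the Background, and nothing says such a claim will rest on the ANOVA p-value.

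Finally, it is tempting to let a one-category improvement define clinical significance. The documents attach that term to the score (Background and section 9.1), and no section says a category shift is clinically meaningful. That choice belongs to the investigators.

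**Conclusion.** The point holds as two linked gaps. First, SA2 has no analysis of its own. If the stated ANOVA is applied to the category codes it is conservative (type I error about 2-3%) and about 5 to 8 power points below an analysis using baseline category.

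These sizes rest on the assumed latent mean, SD and correlation, on 13 evaluable per arm, and on screening and pre-test FSDT being treated as one score. Repeat runs with stratified allocation, some with a 0.3-point control improvement, put the ANOVA's type I error at 2.3-3.0% and its power at 17-24%, 53-60% and 68-75% for the three effects. The gap then ran from about 3 points (27 − 24) to 12 (65 − 53). The direction did not change.

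Second, clinical significance is named without a criterion. That is a matter of text and depends on no simulation. SA1 remains analysable and the sample size is unaffected, so this is a worthwhile improvement and not a fatal flaw.

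**What to change.** Add to section 11.1, as a secondary analysis, that SA2 compares week-8 category (good, moderate, poor) between arms, stratified by or adjusted for baseline category. A mean-score CMH test, a proportional-odds model or a linear model on the codes would serve; name one. Since the Table of Events lists three FSDTs, state that baseline category means the stratum used at randomisation. Report for each arm the proportion improving by at least one category, with the difference and its 95% CI, as description only.

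Separately, have the investigators state and justify, before outcome data are seen, the FSDT score change they will regard as clinically significant. Any such claim should be judged by setting the CI of the between-arm difference in score against that threshold, not by the ANOVA p-value. This review does not propose a value.

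The cost is a few sentences and one further test on data already being collected, with no extra visits or participants. The drawback is that the wide interval on the responder difference will show how imprecise that comparison is at this size.

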2.0 Background*

2.1 Poor biomechanics due to a deficiency of neuromuscular control at the hip contribute to knee joint injuries. Neuromuscular control of the proximal femur plays a key role in tibiofemoral joint positioning.¹ When lacking strength and neuromuscular control of the gluteus maximus (Gmax) and gluteus medius (Gmed), the femur internally rotates and adducts during single-limb movements such as in the Forward Step Down Test (FSDT).² Such movements put the knee into a position of excessive valgus which is a combination of movements: adduction and internal rotation of the femur, abduction of the knee, anterior tibial translation, external tibial rotation, and ankle eversion.³ The combination of these movements increases injury risk at the knee.⁴ The FSTD aims to evaluate several of these movements isolated to the frontal plane which is controlled in majority by the Gmed.

Previous studies have been conducted to explore if different combinations of exercises in a home exercise program (HEP) can help to improve scores on the FDST. These HEPs from past studies included a hip activation program, a combined hip activation and single-leg balance program, and a combined hip activation and core activation program. However, despite increases in activation of the Gmed as seen by surface electromyography (sEMG) data,

there was minimal indication that these programs caused a significant improvement in mean score on the FSDT itself.^{5,6} The hip activation program alone did not cause functional change in the participant's frontal plane movement quality by decreasing their FSDT score a clinically significant amount. It did improve the participants' strength with statistical significance. Training functional movements to improve movement patterns using motor learning while incorporating dynamic hip activation exercises and its effect on the FSDT have yet to be investigated. This study aims to explore the relationship between adding visual and auditory feedback to functional dynamic exercises that activate the gluteal muscles in an HEP and hip activation exercises with scores on the FSDT. Despite the frequent use of the FSDT to look at functional movement patterns in patients, there is still a need for evidence-based interventions that can consistently improve performance on this test which will translate functionally to increased dynamic knee stability.

- 2.2 Our participants will undergo a prescreening utilizing the FSDT. Preliminary data will be used for exclusion, stratification, and randomization of participants. The FSDT is scored on a 0–6-point scale with 0-1 categorically defined as good, 2-3 as moderate, and 4+ as poor movement quality. A participant will be excluded from the study if their score is defined as “good”. Then, stratification will be based upon the participant's categorical FSDT score of either moderate or poor to ensure equal representation of the category in each experimental group. Once stratification is complete, participants will be randomly assigned into two groups. The Control group will receive an HEP focusing on isometric gluteal activation while the Experimental group will receive an HEP focusing on isometric gluteal activation plus movement retraining program. This will be the first study on this topic by the authors. However, two of the authors have done prior research using the FSDT as an outcome measure.^{5,6} Similar FSDT and sEMG procedures will be used as in previous studies. In this investigation we will compare the effects of an isometric gluteal activation HEP vs an isometric gluteal activation plus movement retraining HEP. Outcome measures will include FSDT score and movement quality category, Gmed and Gmax mean and peak activation via sEMG, and compliance measures of both HEP's to evaluate dose response.
- 2.3 The FSDT is a commonly used clinical assessment tool for evaluating lower extremity (LE) strength and function.⁷ It specifically aims to assess postural control, neuromuscular control, and strength of the lower extremity.⁷ Previous studies have found that healthy individuals may not have proper neuromuscular control to manage excessive frontal plane motion during the FSDT.^{5,6} Research has not been conducted to examine how attempting to change or improve individuals' motor programs would affect their performance in the FSDT. Movement retraining could be a way to help improve frontal plane movement quality in individuals undergoing the

FSDT. Movement retraining is defined as a process in which a motor program is changed with the goal of reducing pain or injury risk.⁸

The essential aspect of a movement retraining program is providing feedback during movement execution. The feedback enables individuals to adopt correct movement strategies and develop a sense of proper form. Through these feedback mechanisms, individuals can assess whether they are performing the movement correctly and engaging the appropriate musculature.⁹ This plays a key role in reshaping coordination patterns and promoting transferability of motor learning across different tasks, including applications in lower extremity rehabilitation.⁹ Feedback can be delivered in several categories, including visual, auditory, or haptic forms.⁸ Among these different types of feedback, visual feedback helps the person to identify and correct alignment or movement errors as they execute the movement.¹⁰ This feedback can be portrayed using videos so that the participant can watch someone with proper form to perform the movement. Visual feedback can also be portrayed using mirrors to allow the participant to have knowledge of their form and execution of the movement. Auditory feedback provides external cues describing what the participant should feel or observe while performing an exercise. This reinforces the person's awareness of their movement mechanics. Research supports that external feedback and cueing strategies, particularly auditory and visual cues, enhance motor learning by increasing awareness of body mechanics. It also has the added benefit of improving movement retraining outcomes by allowing the person to have knowledge of their performance and learning how to improve it.¹⁰ Furthermore, evidence suggests that multimodal feedback, combining auditory, visual, or haptic cues, outperforms single-modality feedback by offering complementary information that enhances error correction and overall motor learning. This augmented feedback should complement, rather than replace the body's intrinsic sensory feedback mechanisms.¹⁰

The goal of the exercises added to the HEP combined with the gluteal activation program that has been used previously would be to utilize visual and auditory feedback to give immediate cues to enhance postural control during dynamic functional exercises. The exercises selected are single leg Romanian deadlifts (RDL), split squats, and single leg squats. The selected exercises have shown sufficient activation of the gluteus medius and maximus muscles.¹¹ Specifically, single-limb squats and single-limb deadlifts exercises effectively activated both the Gmed and Gmax.^{12,13} In doing these exercises with feedback, the desired effect would be to increase motor learning in the participants training them how to use the muscles during dynamic exercises that mimic functional movements by doing exercises that increase the activation of the gluteal muscles. By adding the dynamic postural control gained from motor learning and combining these exercises with gluteal activation exercises that have previously shown success in significantly increasing activation could then transfer to improvements in FSDT scores and movement quality in the frontal plane.

Home Exercise programs (HEPs) provide a means to implement an interventional exercise plan to be conducted at the participant's home. Normally, an HEP consists of clear visuals and written instructions that guide the participants in completing the exercise effectively. In utilizing videos, as well as visuals and written instructions in the HEP for this study, the subjects will benefit from both visual and auditory cues given in video form. This combined with visual feedback given by the mirror in front of the participant provides knowledge of their execution of the movement. The cues combined with the knowledge of their performance will help to emphasize correct movement patterns. Research supports the idea that more feedback is not always more helpful when engaging in motor learning. Allowing participants to make and correct their own errors at home helps to support motor learning retention by allowing the participant to self-select the corrections to their movement patterns as they engage in the exercise.¹⁰ The participant is able to do this by attending to and correcting their movement patterns in the mirror as they recognize them. Additionally, the participants will have the ability to control the timing of their feedback. By allowing learner to decide the pace of feedback, evidence shows that it enhances engagement, confidence, and motor learning.¹⁴ However, HEP's rely on patient compliance. Patients are expected to adhere to the program and truthfully document a log of completion. To check compliance, the log can be monitored throughout the process as well as asking the participant to demonstrate the HEP from memory.

Gluteal activation from an isometric activation HEP alone has shown to increase performance on the forward step-down test. However, the improvement was not found to be clinically significant.^{7,8} The aim of this study would be to build on prior research and create a HEP that could be used to show a clinically significant difference in FSDT scores. Over the eight-week intervention, this approach will aim to utilize visual and auditory cueing used during functional dynamic exercises to improve hip activation by increasing postural control which would translate into meaningful improvements in FSDT scores and dynamic knee stability.

